## **Description of Subject Population**

### Sample #1

Specify subject population

Opioid-Dependent Participants with Opioid Use Disorder

Number of completers required to accomplish study aims

16

Projected number of subjects who will be enrolled to obtain required number of completers

32

Age range of subject population

18-55

#### Gender, Racial and Ethnic Breakdown

All efforts will be made to ensure that the representation of women and of ethnic minorities are in proportion to the individuals with Opioid Use Disorder (OUD) in New York City. It is estimated that the sample will be 70% male, 50-40% Caucasian, 45%-40% Black or African American, 0-5% Asian, Pacific Islander and Native American, and 15% will self-identify as multi-racial. We anticipate that  $\approx$  30% of our sample will be of Latino/Hispanic ethnicity. These estimates are based upon data from non-crisis heroin treatment admissions, reported by the New York City Department of Health and Mental Hygiene. <https://ndews.umd.edu/sites/ndews.umd.edu/files/SCS-Report-2018-New-York-City-FINAL.pdf>.

Description of subject population

Healthy participants meeting DSM-5 OUD criteria and physical dependence on opioids will be enrolled.

## Recruitment Procedures

Describe settings where recruitment will occur

Potential applicants will first complete a telephone/videoconferencing assessments during which we will obtain information on demographics, medical, psychological and personal history, as well as details on their use of various prescription and illicit drugs. Participants who pass the initial virtual screening will be scheduled for additional in-person screening procedures at NYSPI. All in-person screening and assessments (medical examination, and naloxone challenge) will occur within the facilities of the Substance Use Research Center (SURC), located on the 3rd floor of the NYSPI. How and by whom will subjects be approached and/or recruited?

Interested participants who respond to study advertisements by call the Opioid Research Lab screening line. A research assistant or volunteer will conduct a general telephone interview to see if they meet criteria for any active studies. These telephone screens are reviewed by a senior member of the research team to determine if further in-person screening is warranted.

How will the study be advertised/publicized?

Recruitment is primarily through word-of-mouth and advertisements in local newspapers such as the Village Voice and AM New York, New York and New Jersey transportation (e.g., Subway and Bus), as well as electronic media (e.g., Facebook, Google, StudyKik) and websites that drug users frequent such as Bluelight and Erowid. The study will be using RecruitMe as a platform for recruitment. This study will be using Moshemu, which specifically targets difficult to reach, stigmatized populations (specifically substance abusers). NIDA is funding the creation of this recruitment platform and the first researchers to sign up will be able to use the platform for free. The Moshemu staff will work to use online recruitment methods to attract potential research participants to the Moshemu platform and guide them through an initial screening process. Next, researchers will be connected with these participants in order to enroll them into their studies.

Do you have ads/recruitment material requiring review at this time?

Yes

Does this study involve a clinical trial?

Yes

Please provide the NCT Registration Number

NCT05114460

## Concurrent Research Studies

Will subjects in this study participate in or be recruited from other studies?

Yes

Describe concurrent research involvement

7680: Assessing the Effects of Heroin Use on Epigenetic Aging (PI: [name] PhD)

6723: Risks and Benefits of Overdose Education and Naloxone Prescribing to Heroin Users (PI: [name].)

7712: Clinical Trials of Multivalent Opioid Vaccine Components.(PI: [name].)

7788: Isolation of opioid-specific B cell lymphocytes and development of human opioid-specific monoclonal antibodies(PI: [name].) A Randomized, Double-Blind, Placebo- and Active-Controlled, Crossover Study to Evaluate the Abuse Potential of Oxymorphone Compared to Other Mu-Opioid Agonists in Physically Dependent Opioid Users with Moderate-to-Severe Opioid Use Disorder (PI: [name].)

## Inclusion/Exclusion Criteria

Name the subject group/sub sample

Opioid Users

Create or insert table to describe the inclusion criteria and methods to ascertain them

Criterion	Method of Ascertainment
1. 18-55 years of age.	Self-reported age and verification with legal identification.
2. Diagnostic criteria for Opioid Use verification with legal identification. Disorder (OUD) moderate-severe (304.00) as per DSM-V, including physiological dependence and not currently seeking treatment for OUD.	MINI Substance Use Module, naloxone challenge/visual evidence of opioid withdrawal.
3. Self-reported opioid use for non- therapeutic purposes; and positive urine drug screen for opioids.	Urine drug toxicology and clinical interviews
4. Physically healthy.	Laboratory tests (urinalysis, blood chemistry & hematology, 12-

	lead ECG), physical examination, and medical history.
5. Body mass index (BMI) $\geq 18$ and $\leq 35$ kg/m  and weight $\geq 50$ kg (110 pounds).	Weight and BMI calculations.
6. Able to perform study procedures.	Practice Session
7. Females must be either: a. Post-menopausal (amenorrhea for at least 12 consecutive months), surgically sterile -or b. Women of childbearing potential must agree to use an acceptable double-barrier method of contraception during screening and study participation.	Urine (Screening) and Serum (Admission Day) pregnancy tests, Nurse's assessment.
8. Must use cannabis products on less than three occasions (occasion= a single administration period of <30 minutes) per week for the four weeks before screening.	Clinical Interviews

Create or insert table to describe the exclusion criteria and methods to ascertain them

Criterion	Method of Ascertainment
1. Seeking treatment for Opioid Use Disorder.	Clinical Interview
2. Current or history of a psychiatric condition that would affect participants' ability to provide informed consent (e.g., mood disorder with functional impairment or schizophrenia) or make participant hazardous for the participant (e.g., recent suicidal ideation) or staff (e.g., significant history of violence).	Beck's Depression Inventory, CSSRS Screener, Psychiatric Examination (with psychiatrist or clinical psychologist)
3. Current DSM-V diagnosis of substance use disorders requiring medically managed detoxification, other than OUD (e.g., alcohol or benzodiazepine dependence).	MINI: Substance Use Module & Clinical Interviews
4. Medical condition resulting in chronic pain ( $>3$ months).	Clinical Interviews, Medical History, Physical Examination.
5. Clinically significant abnormality on physical examination, vital signs, screening laboratory tests, or 12- lead ECG.	Physical examination, vital signs, screening laboratory tests, or 12-lead ECG.
6. Significant cardiovascular, hepatic, renal, respiratory, gastrointestinal, endocrine, immunologic, dermatologic, hematologic, or	Medical History, Physical Exam

neurologic disorder.	
7. Any surgical, or medical condition that may interfere with the absorption, distribution, metabolism, or excretion of the study drugs.	Medical History, Physical Exam
8. Baseline hypotension, orthostatic hypotension or syncope, hypertension (blood pressure $> 140/90$ ), pulmonary hypertension or heart disease.	Medical History, Physical Exam, Nurse's Assessment
9. Any of the following values for laboratory tests: a. positive pregnancy test, b. hemoglobin $< 12$ g/dL in males and $< 11$ g/dL in females, c. neutrophil count $< 1.0 \times 10^9/L$ , d. platelet count $< 75 \times 10^9/L$ , e. creatinine clearance $< 50$ ml/min per modified Cockcroft-Gault equation, f. aspartate aminotransferase or alanine aminotransferase $> 3.0 \times$ upper limit of	Laboratory Testing
10. Hypersensitivity to opioids, history of significant adverse reactions to cannabinoids, and allergy or contraindication to any other drugs administered as a part of this investigation.	Clinical Interviews, Medical History
11. Use of an investigational agent within 30 days.	Clinical Interviews

## **Waiver of Consent/Authorization**

Indicate if you are requesting any of the following consent waivers

Waiver of consent for use of records that include protected health information (a HIPAA waiver of Authorization)

No

Waiver or alteration of consent

No

Waiver of documentation of consent

Yes

Waiver of parental consent

No

## **Consent Procedures**

Is eligibility screening for this study conducted under a different IRB protocol?

No

Describe procedures used to obtain consent during the screening process

**General Telephone Screening:** Participants who respond to study advertisements will complete a general Opioid Research Laboratory Telephone Screener. Verbal consent to complete the telephone screen is noted on the screener form by a volunteer or research assistant. Telephone screens are reviewed by a senior member of the research team to determine if further, study-specific screening procedures are warranted.

**Remote Study-Specific Screening:** Participants who pass the telephone screen will receive a copy of the 8061 screening consent form via an encrypted email (if the participant has email access), to review while the research assistant reviews it with them over the phone. A research assistant, volunteer, nurse, or psychologist will note on a physical copy of the consent form, that verbal consent was obtained to initiate study-specific remote screening procedures. Following screening consent, participants begin remote screening procedures to minimize the number of in-person visits to NYSPI. During remote screening, the participant will complete various screening assessments (e.g., CSSRS, BDI, PhD Interview Nurses assessment) with the research assistant, nurse, or psychologist through HIPAA-compliant platforms such as Zoom or Facetime, or telephone. The investigators will address any concerns the patient may have regarding confidentiality during this process such as access to a private space in which to take calls. These remote assessments are primarily collected in Qualtrics (e.g., PhD Interview, NIDA Assist BDI, and CSSR-S), while some medical history forms are completed on paper by the assessor).

**In-Person Screening:** Prior to their first in-person visit, participants will be informed of the risk of COVID-19 exposure while traveling to, and while at NYSPI. This information is included in the screening consent form. During the in-person visit, the participant will sign a physical copy of the HIPAA form. Participants will be given the option of having the signed copy of the consent form sent to them via email, instead of receiving a physical copy.

**Describe Study Consent Procedures**

The study consent will have been reviewed with the participant extensively over the phone, during the screening phase of the study. A research assistant (BA/BS) will read the consent form verbatim. The participants will be offered the opportunity to ask questions of an investigator or physician during each of the in-person screening visit(s), and again when they meet with the MD or NP, who will conduct the consenting process. A physical copy of the study consent will be signed with a physician or NP on the day of admission (or the final day of screening). The physician or NP will review the inclusion/exclusion criteria, comparing it to the participant's screening data, prior to obtaining study consent. Participants will be given the option of having the signed copy of the consent form sent to them via encrypted email, instead of receiving a physical copy.

**Waiver of Documentation of Consent**

Would the consent form signature be the only link between the subject's identity and the research data?

No

Is breach of confidentiality the main study risk?

No

Is consent for this research procedure ordinarily not required outside of the research context? Explain

We would like to request a waiver of documentation of consent via 45CRF46.117(c), for the study-specific Remote Screening Procedures. Following a brief general telephone screener, some of the study-specific screening procedures will be conducted remotely, potential participants will review the approved screening consent form, but we will not be obtaining their signature. Instead, the staff member who reviews the consent form with the participants and obtains their verbal consent, will document and attest that verbal consent was obtained on the screening consent form. Study Consent will be documented with the participant and physician's (or Nurse Practitioner's) signature.

## Study Procedures

Describe the procedures required for this study

Screening: Healthy adults with Opioid Use Disorder will be recruited for this study in accordance with the Inclusion/Exclusion criteria, using the measures outlined in the "Assessment Instruments" section of the PSF. After reviewing screening results, a physician and the study PI will make the final decision as to whether the participant is eligible for the study.

To minimize the number of visits to NYSPI (minimizing the risk of COVID-19 exposure for participants and staff), some screening measures will be conducted via telephone, Zoom, or Facetime (only HIPAA-compliant, CUIMC accounts will be used). Study staff (research assistant, nurse, or psychologist) will simultaneously complete paper copies, based on the subjects' responses, or enter data directly into the appropriate electronic data capture system (e.g., Qualtrics- which will contain no PHI).

This study requires that some screening procedures occur on-site (e.g., physical, psychiatric evaluation, ECG, bloodwork). One of the final screening assessments will be the naloxone challenges (to verify opioid dependence). This test will only be performed after the other screening assessments have verified that the participant is sufficiently healthy to minimize the risk of this procedure. The day prior to their in-person visit(s), a research assistant or nurse will complete a COVID-19 symptom screener. Additionally, a test for the presence of COVID-19 and/or its antibodies will be performed prior to admission. As with any significant lab results, a member of the medical team will disclose and discuss a positive COVID-19 test result, and provide appropriate treatment referrals.

**Admission and Morphine Stabilization:** Once eligibility is determined, participants will be admitted into the secure NYSPI inpatient unit for the duration of the study (approximately 4 weeks). Following admission, participants will begin 5-14 days of stabilization on oral morphine (30 mg, QID: 700, 1300, 1800, 2200 hrs). Additionally, 10-20mg PO hydromorphone doses will be available PRN to address withdrawal symptoms insufficiently managed by oral morphine and supplemental medications alone (to a maximum of 80 mg per day). Hydromorphone will be available in addition to QID oral morphine when deemed clinically appropriate by the study physician. **The participant must exhibit at least "mild" opioid withdrawal according to the COWS (score >8).** Once stabilized, participants will receive oral morphine daily (30 mg) at 700, 1300, 1800, and 2200 hrs. **Prior to the initiation of testing sessions, stability on morphine will be established. Stability will be defined as participants exhibiting a mean COWS score not exceeding 5, with no hydromorphone administration.** Vitals and Respiratory Rate will be assessed immediately before and for one hour (in 15-minute intervals) following the additional dose to ensure against oversedation.

Common clinically used medications such as, clonidine, zolpidem, and Compazine will be available, along with methocarbamol (750-1500 mg, every 6 hours, not exceeding 6000mg in 24 hours). The use of these medications will be suspended by 6 PM the day before a lab session. Participants who cannot stabilize and will be discharged and offered the same end-of-study treatment options described below.

**Safety Session:** Testing will not begin until withdrawal symptoms are no longer present, based upon the Clinical Opioid Withdrawal Scale (COWS: Handelsman et al., 1987). Prior to testing vaped marijuana in combination with intranasal (IN) naloxone, participants will complete a Safety Session. During the safety session, they will receive a test dose of vaped marijuana (25 mg). If a participant's vital signs exceed any of the following benchmarks outlined in the Criteria for Early Discontinuation, they will be discontinued from the trial (Table 1).

Table 1: Study Design														
Week 1							Week 2							
	Mon	Tue	Wed	Thu	Fri	Sat	Sun	Mon	Tue	Wed	Thu	Fri	Sat	Sun
	Admission	Stabilization	Stabilization	Stabilization	Stabilization	Stabilization	Stabilization	Stabilization	Stabilization	Stabilization	NLX 0mg + V-MJ 0mg	NLX 4mg + V-MJ 25mg		
Week 3							Week 4							
	NLX 0mg + V-MJ 12.5mg	NLX 0mg + V-MJ 25mg	NLX 4mg + V-MJ 12.5mg	NLX 4mg + V-MJ 0 mg			Discharge							

**Laboratory Testing:** Laboratory testing sessions will consist of a modified naloxone challenge procedure (A.K.A. Wang Test: Wang et al., 1974). The challenge begins with baseline assessments. Ten common symptoms of opioid withdrawal (gooseflesh, vomiting, tremor, sweating, restlessness, lacrimation/nasal congestion, yawning, warming/cooling sensations, stomach pain, and muscle ache) will be assessed by a research assistant trained in administering the SOWS/COWS. For safety, the physician or nurse who is providing medical oversight will directly observe its administration.

Each symptom is coded as either “absent” or “present,” with between 1 and 6 points added when a symptom is observed (Table 2). Following pre-test assessments, a physician or nurse practitioner will administer the study drug combination (1000-1100 hrs). Assessments of withdrawal are made at 10-minute intervals for 50 minutes. The total withdrawal score is calculated at the end of the session. To minimize carry-over effects, sessions will be conducted at least 48 hours apart (>5 half-lives of both medications). See Table 1 for an example dosing schedule. The following dose combinations of vaped marijuana (V-MJ) and IN naloxone will be tested in random order:

- Naloxone 0 mg + V-MJ 0.0 mg
- Naloxone 0 mg + V-MJ 12.5 mg
- Naloxone 0 mg + V-MJ 25 mg
- Naloxone 4 mg + V-MJ 0.0 mg
- Naloxone 4 mg + V-MJ 12.5 mg
- Naloxone 4 mg + V-MJ 25 mg

Signs and Symptoms	Table 2: Rating Scale for Opioid Withdrawal											
	(Pre-test)		Time after first naloxone dose									
	0 min		10 min		20 min		30 min		40 min		50 min	
Signs and Symptoms	Present	Absent	Present	Absent	Present	Absent	Present	Absent	Present	Absent	Present	Absent
Gooseflesh	6	0	3	0	3	0	2	0	1	0	1	0
Vomiting	6	0	3	0	3	0	2	0	1	0	1	0
Tremor	6	0	3	0	3	0	2	0	1	0	1	0
Sweating	6	0	3	0	3	0	2	0	1	0	1	0
Restlessness	4	0	2	0	2	0	1	0	1	0	1	0
Lacrimation/ Nasal Congestion	4	0	2	0	2	0	1	0	1	0	1	0
Yawning	4	0	2	0	2	0	1	0	1	0	1	0
Feeling of Change in Temperature	3	0	1	0	1	0	1	0	1	0	1	0
Stomach Pain	3	0	1	0	1	0	1	0	1	0	1	0
Muscle Ache	3	0	1	0	1	0	1	0	1	0	1	0
Actual time of observation												
Scores												
Pupil Diameter												

Vaping of cannabis provides a rapid and efficient method of drug delivery from the lungs to the brain (Abrams et al., 2007; Azofeifa et al., 2016). This investigation will use the MIGHT Vaporizer (manufactured by Stoke and Bissel), which allows for precise temperature control of hot air convection heating. The device will be set to 210°C. Co-investigators ([name] and [name]) currently use this device and are confident in its safety and biocompatibility. A clinical trial from Australia (Arkell et al., 2019), utilized the Mighty Medic device to administer 125 mg THC (11%) to healthy volunteers. Same percentage as the current trial, but a lower dose. AEs were minimal (increased self-reports of being “Sedated” and “Anxious”). Furthermore, Carra et al., (2020) characterized the delivery kinetics, efficiency, and decarboxylation yields of the Mighty Medic for delta-9-tetrahydrocannabinol and cannabidiol. Thus, the investigators are confident that the proposed doses of vaped MJ will be pharmacodynamically efficacious and well-tolerated.

**Dose Rationale:** The naloxone dose selection was based on the purpose-designed, overdose first-aid drug Narcan® Nasal Spray (4mg/0.1ml).

The V-MJ doses were selected based on proposed efficacy and safety. In a recent trial, Spindle et al., (2018) conducted a controlled examination of the effects of vaporized and smoked cannabis in “infrequent” cannabis users (N=17). For vaporized conditions, mean peak plasma concentrations for THC were 7.5 ng/mL at the 10-mg dose and 14.4 ng/mL at the 25-mg dose. Among these normal health volunteers, modest impairment of cognitive functioning and psychomotor agitation (e.g., significantly decreased task performance) were the most common adverse events.

\*Please Note\* A 2 mg naloxone dose condition was dropped on the recommendation of the NIDA

scientific officer.

During the Lab session, additionally, adverse events (AEs) unrelated to withdrawal will be quantified using the Systematic Assessment for Treatment Emergent Events (SAFTEE: Levine and Schooler, 1986). Pupil diameter will be measured using a Neuroptics® digital pupillometer. Heart rate (HR) and blood pressure (BP) will be measured using a Criticare® vital signs monitor and recorded at 15-min intervals. For safety, vital signs (HR, BP, and pulse oximetry) will be monitored every 5 minutes for the first 30 minutes, then every 15 minutes for the next 1.5 hours at which point THC plasma concentrations should be negligible. Additional vital monitoring will occur every 30 minutes for the next 2 hours, for a total of 4 hours of post-dose monitoring. In the Criteria for Early Discontinuation section, we have outlined vitals parameters that will preclude a participant from completing additional sessions and discontinue their enrollment in the trial.

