## Lay Summary of Proposed Research

### Lay Summary of Proposed Research

To address the opioid epidemic, there has been an increased focus on the development of novel medications to treat opioid use disorder (OUD). However, a pharmacological approach more specific to overdose harm reduction (i.e., minimizing the harmful effect of drugs among active users) may be to increase the tolerability of the overdose reversal agent, naloxone (NLX). In emergency settings, NLX administration (in suspected cases of opioid overdose) often results in violent patient behavior, as individuals who are opioid dependent awaken in a state of opioid withdrawal (Gaddis and Watson, 1992; Osterwalder, 1996).

Naloxone-induced withdrawal is also common in out-of-hospital settings in which non-medical persons are asked to administer naloxone to save the lives of their peers. Analysis of the Opioid Lab's overdose reports from the individual who administered NLX found that 98% of overdose victims presented notable opioid withdrawal-related adverse events (AEs) including: nausea, abdominal pain, vomiting, joint/muscle pain, and tremor. Concerns of the adverse effects of NLX administration may prevent or delay the use of this life-saving intervention.

The goal of the proposed, proof-of-concept study is to test the combined effects of vaporized marijuana [Delta-9-tetrahydrcannabinol (THC)] with NLX as a proof of concept towards the possible development of a combined overdose reversal agent with improved tolerability. Marijuana will not actually be vaped per se, but a “vaporizer” will be used to produce an aerosol from marijuana plant material, which the participant will inhale. Marijuana plant material will be obtained from the National Institutes on Drug Abuse (NIDA). In clinical studies, oral synthetic THC (Bisaga et al., 2015; Lofwall et al., 2016) reduced the severity of opioid withdrawal during opioid detoxification (Scavone et al., 2013). Clinically, cannabinoid drugs like Marinol® (oral synthetic THC), Sativex ® (nabixomols), and Cesamet® (nabilone) are used to treat nausea and vomiting, common symptoms of opioid withdrawal. This study will investigate the ability of vaporized marijuana (V-MJ) (0.00, 12.5, and 25 mg; concentration= 11.7% THC + 0.04% CBD.) to reduce the severity of opioid withdrawal precipitated by intranasal (IN) NLX (0.0 and 4.0 mg). The final dose of marijuana will be achieved in 10 puffs/vapes, in 10-12 minutes (at a temperature of 210°C).

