**Additional Assessments During Laboratory Sessions (completed at -30, +15, +30, +45, +60):**

- The subjective effects battery will consist of Visual Analog Scales and the Opioid Craving Questionnaire (Tiffany et al., 1993),
- Two cognitive tasks will be used in the proposed studies. The Digit Symbol Substitution Task (McLeod et al., 1982) and the Divided Attention Task assesses attention (DAT; Miller, 1987).
- Brief Psychiatric Rating Scale (BPRS) will be performed at +45

At the end of the test testing session, the participant may receive a rescue dose of oral morphine (30 mg). If COWS scores remain >5 at the next measurement timepoint (+15 minutes) an additional 20 mg may be provided, at the discretion of a study physician. The testing session may also be terminated 20 minutes following naloxone administration (if withdrawal is too severe (COWS >20) and the rescue dose given at this time. A physician, nurse practitioner, or nurse will be notified once the COWS score goes above 9.

The RA will notify the physician/nurse practitioner once the criterion for the morphine rescue has been met, who will then administer the rescue dose. If a morphine rescue is given, vital signs will continue to be monitored for the entire 4-hour period. If a participant receives a rescue dose during the testing session, the 1 pm morphine dose may be held at the discretion of the physician.

Suicidality and Pregnancy will be monitored weekly throughout the inpatient period using the CSSRS and a urine pregnancy test, respectively.

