## **Criteria for Early Discontinuation**

### Criteria for Early Discontinuation

#### Do Not Administer Vaped Marijuana (T: -15 mins) if:

- Systolic BP<110 or > 150 mm Hg; Diastolic BP < 60 or >90 mm Hg, or Heart Rate< 60 or >110 BPM

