#### Do Not Administer Naloxone (T: 0 Mins) if:

- Systolic BP<110 or > 150 mm Hg; Diastolic BP< 55 or >95 mm Hg, or Heart Rate< 60 or >110 BPM

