Randomization: Once a participant is enrolled, a randomization sequence table will be generated by a blinded statistician. The table will determine the order of testing of the various dose combinations of dronabinol (.00, .35, and .70 mg), and naloxone (0.0, 0.2 and 0.4 mg).

Aims, Outcome Measures, and Hypotheses

Primary Aim: Assess the ability of inhaled dronabinol to alter the severity of naloxone-precipitated withdrawal.

- The primary dependent variable (DV) for this aim will be the total opioid withdrawal score from the testing session. Repeated-measures analysis of variance (ANOVA) will be used to assess differences among the various dose conditions.
- We hypothesize that there will be a dose-dependent effect of dronabinol to attenuate the severity of naloxone-precipitated withdrawal.

Secondary Aim: Assess the safety of inhaled dronabinol in combination with naloxone.

- The primary DVs are the SAFTEE (AEs not related to withdrawal) and physiological parameters. Generalized mixed-effects models with participant as a random effect and an autoregressive correlation structure for the within-participant observations will be used to analyze the total number of AEs and their severity.
- We hypothesize that dronabinol, in combination with naloxone, will produce more AEs than placebo but less than naloxone alone.

Secondary Aim: Assess the impact of inhaled dronabinol on naloxone's effects on pupil diameter (i.e., μ -opioid receptor blockage).

- The primary DV will be pre-to-post- medication change in pupil diameter from each testing session. Repeated-measures ANOVA will be used to assess differences among the various dose conditions.
- We hypothesize that dronabinol will not significantly alter naloxone's effects on pupil diameter (in comparison to placebo).

Secondary Aim: Assess the abuse potential of inhaled dronabinol.

- The primary DV will be pre-to-post- medication change in positive subjective drug ratings such as drug "Liking" and "Good Effect."
- We hypothesize that self-reported dronabinol "Liking" will not be significantly greater than placebo.

Power

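### The primary withdrawal total takes in up to 45 points scored before naloxone; the column's timing is unclear and the stated 0-125 range does not match Table 2

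*Protocol*

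**What the plan says.** Under Laboratory Testing (Protocol, Study Procedures), the session opens with baseline assessments and dosing follows: "Following pre-test assessments, a physician or nurse practitioner will administer the study drug combination (1000-1100 hrs". The two drugs are treated as one administration. Each symptom present adds 1 to 6 points, and "The total withdrawal score is calculated at the end of the session". No sentence lists the columns that make up the total.

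Table 2 has a pre-test column labelled 0 min. The 10-50 min columns follow under "Time after first naloxone dose". Pupil diameter is a row of the same table.

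The order of the two drugs appears only in the hold rules under Criteria for Early Discontinuation: "Do Not Administer Vaped Marijuana (T: -15 mins) if" and "Do Not Administer Naloxone (T: 0 Mins) if". The Lay Summary gives the inhalation time: "The final dose of marijuana will be achieved in 10 puffs/vapes, in 10-12 minutes". The one assessment with an explicit time before V-MJ is the subjective and cognitive battery: "Additional Assessments During Laboratory Sessions (completed at -30, +15, +30, +45, +60".

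The SAP, which still names inhaled dronabinol where the protocol has V-MJ, takes the session's total withdrawal score as the primary outcome. Its Power section gives that score a range of 0-125, with a 15-point design difference and an SD of 20. The pupil outcome is the "pre-to-post- medication change in pupil diameter from each testing session".

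**The concern.** The primary aim is whether V-MJ reduces withdrawal precipitated by naloxone. Signs recorded before naloxone cannot carry that effect, yet they are added to the score, and at the largest weights in the table. Gooseflesh at pre-test scores 6, as much as gooseflesh at both 10 and 20 min (3 + 3). Because the points are added rather than subtracted, a participant who starts a session with symptoms is scored as having had more severe precipitated withdrawal.

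What the extra points measure depends on when the reading is taken. Before V-MJ, they are session-to-session variation unrelated to that day's treatment. At 0 min on the naloxone clock, V-MJ has already been inhaled, and the points also hold whatever V-MJ itself does to the scored signs.

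The pupil outcome has the same gap. Two medications are given about 15 minutes apart, and the SAP does not say which one the baseline precedes. Effect-size estimates are the main result for the secondary aims, so the baseline should be fixed in advance.

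**Working it through.** **1. Column maxima, from the Present weights in Table 2.** Four items carry the first weight (gooseflesh, vomiting, tremor, sweating), three the second (restlessness, lacrimation/nasal congestion, yawning) and three the third (temperature change, stomach pain, muscle ache).

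| Reading | Weights | Maximum |
|---|---|---|
| Pre-test (0 min) | 6, 4, 3 | 4×6 + 3×4 + 3×3 = 45 |
| 10 min | 3, 2, 1 | 12 + 6 + 3 = 21 |
| 20 min | 3, 2, 1 | 21 |
| 30 min | 2, 1, 1 | 8 + 3 + 3 = 14 |
| 40 min | 1, 1, 1 | 10 |
| 50 min | 1, 1, 1 | 10 |

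- After naloxone: 21 + 21 + 14 + 10 + 10 = 76.
- All columns: 76 + 45 = 121.
- The SAP's maximum of 125 does not reproduce. It is 4 above the full sum and 49 above the post-naloxone sum.

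**2. Does the pre-test column count?** Two facts say yes. The scoring sentence allows up to 6 points per symptom, while no weight after naloxone exceeds 3, so weights of 4 and 6 come only from the pre-test column. And a maximum near 125 cannot be reached from 76. Pre-test points are then up to 45/121 = 37% of the attainable total.

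**3. When is the reading taken?** If inhalation starts at T -15 and lasts 10-12 min, it ends at T -5 to T -3; if it starts as late as T -12, it can end at T 0. A reading at 0 min would therefore fall about 0-5 min after V-MJ. A reading before the combination falls at T -15 or earlier. No section gives a clock time for the pre-test withdrawal or pupil reading.

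**4. Scale of one symptom.** One pre-test symptom is worth 3 to 6 points, which is 3/15 = 20% to 6/15 = 40% of the design difference in that session. This is a per-session figure, not an expected mean shift.

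**5. Effect on the primary contrast (V-MJ 25 mg + naloxone 4 mg against V-MJ 0 mg + naloxone 4 mg).** Let D be the within-person difference between the two sessions.

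- D(total) = D(post) + D(pre).
- Pre-test before V-MJ: the mean of D(pre) is 0, so the expected difference is unchanged. Var D(total) = Var D(post) + Var D(pre) + 2 Cov, so the pre-test adds variance unless the covariance is below -Var D(pre)/2.
- Pre-test at 0 min: the mean of D(pre) is V-MJ's own effect on the scored signs before naloxone, and the contrast shifts by that amount. The documents give no value.

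**6. Pupil aim.** With a pre-V-MJ baseline, the simple contrast at naloxone 4 mg includes V-MJ's pupil change up to T 0; with a T 0 baseline it does not. The interaction is [(V25,N4) - (V0,N4)] - [(V25,N0) - (V0,N0)]. V-MJ's change up to T 0 has the same expectation in the naloxone 0 mg and 4 mg sessions, because naloxone has not yet been given, so it cancels whichever baseline is used.

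**The case against.** The best defence is that the text already settles the timing. The session begins with baseline assessments, dosing follows them, and the SAP speaks of change from before medication. The same SAP phrase is used for Liking, whose first reading is at -30. In Table 2 the 0 min label sits under the pre-test heading rather than under the naloxone-time heading, and the form may be carried over from the naloxone-only challenge used at screening. It also has a row for the actual time of each observation. This stands: before V-MJ is the more natural reading, and the table label is what needs correcting.

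Pre-test scores should also be low. Stability requires a mean COWS of at most 5, and the Safety Session paragraph says testing waits until withdrawal symptoms have gone. So 45 is a ceiling, not a likely value.

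A reader might go further and infer that V-MJ contaminates the primary result. Assuming, say, that V-MJ relieves half to one pre-test symptom on average would give false-positive rates of 7.1% to 13.5% (n = 16, paired SD 20). The documents do not support those shifts: participants meant to be free of symptoms have little to relieve. In the other direction, the nearest documented figure is one of 17 participants vomiting after 25 mg vaporized in a cited study. Even if that always fell before T 0, it is 1/17 × 6 = 0.35 points, or 2.4% of 15. Nor is the randomized comparison confounded under either timing; only what it estimates changes.

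What the defence does not answer is that points unrelated to naloxone are in the total under either timing, and that the stated range fits no sum of the table.

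**Conclusion.** The point holds as one of outcome definition. The primary total includes up to 45 of 121 points recorded before naloxone. They add noise if read before V-MJ, and also V-MJ's own effect if read at 0 min. Counting of the column is inferred from the 1-to-6-point rule and the stated range, since no sentence lists the summed columns, but the inference is strong. The size in practice is not given and is probably small.

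The 0-125 range is wrong on either scoring (121 or 76), which leaves it unclear to which scale the 15-point difference and SD of 20 belong.

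For the pupil aim, the baseline matters to a simple contrast but not to the interaction. A reader might conclude that a further reading at T 0 is required; because the change up to T 0 cancels from the interaction, it is not.

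**What to change.** **Protocol, Laboratory Testing and Table 2.** Label the pre-test column as before V-MJ, and state that its withdrawal and pupil readings are completed before the T -15 vital-sign check. Dosing times and hold rules stay as they are.

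**Primary score.** Define it as the sum of the 10-50 min readings (0-76). Use the pre-test score as a session baseline covariate or report it separately. The covariate is sound only once the reading is fixed before V-MJ; at 0 min it would adjust away part of the treatment's effect. Keep the full 0-121 total as a sensitivity analysis.

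**SAP, Power.** Replace 0-125 and restate the 15-point difference and SD of 20 for the chosen scale, ideally recomputed from the earlier data.

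**SAP, pupil aim.** Define change from the pre-V-MJ reading and test whether V-MJ alters naloxone's effect by the V-MJ x naloxone interaction, using the naloxone 0 mg conditions already in the design.

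**Cost.** Wording only; no added reading or visit. The interaction is less precise than a simple contrast: with equal variances and correlations across sessions, its variance is 4σ²(1-ρ) against 2σ²(1-ρ), so the standard error is √2 = 1.41 times as large. The 0-76 score is also less directly comparable with the laboratory's earlier totals, which is why the full total is kept alongside.
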